This is an open-label, single-institution, Phase 2 study to determine the response rate of BXCL701 administered orally and daily, combined with pembrolizumab, in patients with advanced solid cancers. The study will also assess other efficacy parameters, such as progression free survival (PFS), overall survival (OS) and (DOR), as well as the safety the combined treatment. Bayesian optimal phase 2 (BOP2) design will be adopted to monitor efficacy. The study will consist of 2 stages:

- Lead-in Stage (first 6 patients enrolled) in which the safety and tolerability of the combination of BXCL701 administered orally daily on Days 1 to 14 of a 21-day cycle plus pembrolizumab 200 mg administered intravenously (IV) on Day 1 every 21 days will be assessed and confirmed in patients with advanced solid cancers. The dose of BXCL701 will be 0.6 mg in two doses (0.3 mg twice a day).
- 2. Efficacy Stage (BOP2 Stage) in which patients with advanced solid cancers will be treated with BXCL701 combined with pembrolizumab. Patients enrolled to the Lead-in Stage will be also evaluated in the efficacy stage. Starting from Protocol version 7, new patients enrolled will be administered BXCL701at the starting dose of 0.2 mg orally twice a day for the first 7 days. If well tolerated and in the absence of signs and symptoms of clinically significant hypotension the dose will be escalated to 0.3 mg orally twice a day.

Summary of the Study Objectives

Primary objectives

• To evaluate response rate per RECIST and iRECIST in patients treated in cohort A and in patients treated in cohort B.[19, 20] Tumor measurements will be in QIAC.

• To evaluate dose-limiting toxicities (DLT) in the first 6 patients enrolled to the study.

Secondary objectives

• To evaluate progression-free survival (PFS), overall survival (OS), duration of response, and overall safety and tolerability.

Exploratory objectives

- To evaluate the quantitative and qualitative effects of BXCL701 in combination with pembrolizumab on relevant immune effector cells and cytokines in tumor tissues and blood, respectively.
- To explore the predictive value of baseline PD-L1 tumor expression and tumor mutation burden (TMB) with clinical outcomes
- To evaluate changes in serially collected blood circulating tumor DNA (ctDNA) to assess for tumor response and clonal evolution
- To evaluate pre- and post-treatment PD-L1 PET/CT as a predictive tool for therapeutic efficacy.

1 INTRODUCTION

Development of immune checkpoint inhibitors revolutionized treatment of many hard to treat cancers such as melanoma, non-small cell lung cancer, urothelial cancers, kidney cancers, MSI-high colorectal cancers and others. Nevertheless, reported response rates typically range from 13% to 30% for PD1/PD-L1 antibodies and up to 50% for combination of CTLA-4 antibody ipilimumab and PD1 antibody nivolumab.[1-8] In addition, a number of cancers such as MSS colorectal cancer, most of soft tissue sarcoma, prostate cancer, pancreatic cancer and others do not respond to immunotherapy.[9-13] Resistance to immune therapy can be driven by exclusion of CD8+ T-cells and other immune cells or absence of immune cells (immune desert).[14] Activation of innate immunity can activate type I interferon response and increase sensitivity to immune checkpoint inhibitors.[15] We hypothesize that BXCL701 is a competitive inhibitor of DPPs that can induce innate immune reaction and tumor inflammation, leading to synergistic anticancer activity when combined with the immune checkpoint PD1 targeted antibody pembrolizumab.

1.1 BXCL701 Mechanism of Action

BXCL701 is a competitive inhibitor of DPPs, including DPP4 (CD26), DPP8, and DPP9, members of the postprolyl-cleaving protease family. By inhibiting DPP8 and DPP9, BXCL701 treatment results in robust immunostimulation via several mechanisms. One such mechanism is by inhibiting DPP8 and DPP9 in macrophages in the tumor microenvironment and lymph nodes, which, in turn, release interleukin (IL)-1 β , a potent activator of immune effector cells that release numerous other cytokines and chemokines that contribute to anti-tumor activity.

BXCL701 has also been shown to inhibit FAP, which has previously been described as a type II membrane protein with DPP and gelatinase activity. Studies of FAP have reported that FAP expression is induced in fibroblasts associated with the stroma of malignant epithelial tumors. These reports suggest that FAP does not appear to be expressed constitutively in most healthy tissues of the adult animal; however, experiments have demonstrated the expression of FAP in bone marrow and lymphoid tissue from both healthy and tumor-bearing mice. FAP, as well as DPP8 and 9, are expressed and activated in a wide range of malignancies, especially CRPC, that emerge following treatment of CRPC with second generation anti-androgen (enzalutamide) or cytochrome P450 (CYP)17 (abiraterone) inhibitors. Resistance to androgen ablation therapy also results in the expression of PD-L1 and the targets of BXCL701, particularly FAP, DPP8 and DPP9. In animal models with fully intact immune systems, BXCL701 and programmed cell death 1 (PD-1) inhibitors resulted in synergistic anti-cancer activity. To date, BXCL701 has been administered to more than 700 individuals, including 585 cancer patients.

1.2 Preclinical Pharmacology

In a purified enzyme system, BXCL701 inhibits DPP4/CD26 and FAP activity with half maximal inhibitory concentration (IC_{50}) values of 1.0 and 32.0 nM, respectively, while inhibiting DPP8 and DPP9 with IC_{50} values of 2.7 and 3.2 nM, respectively. DPP4/CD26 is a serine protease expressed on a variety of tissues, including T-lymphocytes, endothelial

and epithelial cells, and has been shown to play an important role in tumor progression. It has been found to be expressed in non-small cell lung cancer (NSCLC), chronic lymphocytic leukemia (CLL), lymphoma, and melanoma. In 1 series, 93% of all cases of lung adenocarcinomas were positive for aberrant DPP4/CD26 activity (see Investigators Brochure).[16]

FAP is a type II integral membrane glycoprotein belonging to the serine protease family. It is a 95-kD cell surface glycoprotein expressed by tumor stromal fibroblasts. FAP is well expressed by reactive stromal fibroblasts in more than 90% of human epithelial carcinomas (breast, lung, colorectal, ovary) as determined by immunohistochemistry. In an evaluation of a series of malignant tumors, FAP was expressed in the stroma of all 13 lung tumor samples that were examined. Neural and lymphoid cells, as well as surrounding normal tissue, do not express FAP. FAP expression in normal tissue has only been observed in a subset of pancreatic endocrine cells, bone marrow stromal cells, and transiently in healing wounds. Epithelial carcinoma cells are also FAP-negative, making FAP an attractive target for the study of tumor stromal cell biology. Stromal cells residing in colorectal adenomas are also predominantly FAP-negative, suggesting that malignancy is required for effective FAP induction. Some bone and soft-tissue sarcomas are also known to express FAP, consistent with FAP's mesenchymal origin. Thus, FAP is selectively expressed by tumor stromal fibroblasts in epithelial carcinomas, but not by epithelial carcinoma cells or normal fibroblasts.[17]

DPP8 and DPP9 are expressed widely in a number of tissues, but notably in monocytes and macrophages, where their inhibition with BXCL701 has been compared to the action of an immune checkpoint inhibitor through the activation of an immunogenic cell death called pyroptosis.[18] Current checkpoint inhibitor based therapies largely target T-cells, members of the adaptive immune system, while monocytes and macrophages belong to the innate immune system. Thus, it is an attractive approach to target the cells of the innate immune system, using BXCL701 as a single agent, or even more compelling to use BXCL701 in combination with checkpoint inhibitors targeting the adaptive immune system.

In syngeneic mouse models utilizing the WEHI 164 fibrosarcoma cell line, BXCL701 significantly inhibited tumor growth, both as single agent and in combination with chemotherapies. BXCL701 also significantly inhibited the growth of a human osteosarcoma, SK-ES-01, in mouse xenografts (see Investigators Brochure). A study conducted in a mouse model of metastases using a sarcoma cell line at the National Cancer Institute showed that BXCL701 substantially reduced the number of lung metastases in mice (see Investigators Brochure). The supporter has further demonstrated potent activity of BXCL701 in combination with other immune modulating agents including adaptive immune cell checkpoint inhibitors (e.g., anti-PD-1) in several other models. Notably, in these animal models, tumor response was complete and durable, resulting in the generation of a functional memory T-cell response. This is the case because challenge with the same cancer cells resulted in the failure of a subsequent tumor to form in animals that had generated a durable response.

Thus, preclinical data from the literature and generated by the supporter support the use of BXCL701 as a multimodal DPP inhibitor targeting distinct, yet complimentary, mechanisms in the biology of a cancer.

1.3 Clinical Experience

BXCL701 has been administered to more than 700 human subjects in Phase 1, 2, and 3 clinical trials. Edema and fatigue were the most common adverse events (AEs) seen in these trials.

1.3.1 Healthy Volunteers

Two placebo-controlled Phase 1 studies were conducted in 120 healthy male volunteers (out of which 90 received BXCL701). BXCL701 was well tolerated at single daily doses up to 2.4 mg and when administered as a single daily dose for 7 days at doses up to 1.8 mg. In the single-dose tolerance study, the most frequently occurring AEs in BXCL701 treated subjects were: sensation of temperature change (12/54, 22.2%), tachycardia (11/54, 20.4%), dizziness (8/54, 14.8%) versus 11.1%, 0%, and 0%, respectively, in the placebo group. There were no serious adverse events (SAEs). In the multiple-dose tolerance study, the most frequently occurring AEs in BXCL701 treated subjects were: headache (18/36, 50.0%); temperature change sensation (13/36, 36.1%); myalgia (8/36, 22.2%); nausea (6/36, 16.7%); vomiting (5/36, 13.9%); peripheral swelling (5/36, 13.9%); and sore throat (4/36, 11.1%) versus 41.7%, 0%, 16.7%, 0%, 8.3%, 8.3%, and 0, respectively in the placebo group.

In both studies, BXCL701 significantly increased plasma IL-6 and inhibited plasma DPP-4 activity at single doses ≥ 1.2 mg. Plasma levels of BXCL701 in the multiple-dose study suggest a multi-compartmental distribution. The initial distribution phase was approximately 12 hours. Maximum plasma concentration (C_{max}) appeared to be dose-proportional. Time to maximum plasma concentration ranged from 1 to 2 hours postdose. The plasma half-life was not calculated due to a prolonged elimination phase extending past Day 7. It is thought that BXCL701 binds irreversibly to plasma proteins and that this binding is responsible for the long half-life.

1.3.2 Phase 1 Studies in Patients

BXCL701 was evaluated in 2 Phase 1 studies: in combination with myelosuppressive chemotherapy in 34 patients with chemotherapy-induced neutropenia at doses up to 1.2 mg/day and in combination with rituximab in 20 patients with B-cell malignancies (non-Hodgkin's lymphoma [NHL] or CLL) at doses up to 0.8 mg/day.

Overall, BXCL701 was well tolerated in both the studies. Edema was the most common AE in both studies (45% and 41%). Other AEs when BXCL701 was administered in combination with myelosuppressive chemotherapy included hypotension (including orthostatic) 10/34 (29%) versus 4/41 (10%); anorexia 5/34 (15%) versus 2/41 (5%); and hypovolemia 4/34 (12%) versus 0. In the B-cell malignancy study with BXCL701 administered in combination with rituximab, other AEs included nausea and fatigue (each in 9 patients, 45%); dizziness (8 patients, 40%); constipation and vomiting (each in 6 patients, 30%); and pyrexia, rigors, and thrombocytopenia (each in 5 patients, 25%).

Efficacy results revealed a relatively consistent 1-day reduction in the total number of days of Grade 4 neutropenia at doses from 0.2 to 0.8 mg, whereas no consistent changes in the median or mean number of days of Grade 3 neutropenia were observed. In the B-cell malignancy study, 2/20 (10%) patients were considered to have a partial response (PR).

1.3.3 Phase 2 studies

BXCL701 was evaluated in 6 Phase 2 studies: 54 patients in combination with rituximab in advanced CLL at daily doses of 0.6 mg, as a single agent in 42 patients with metastatic melanoma at doses up to 0.8 mg/day, 55 patients with NSCLC in combination with docetaxel at doses up to 0.6 mg/day, 74 patients with metastatic melanoma in combination with cisplatin at doses up to 0.8 mg/day, 68 patients with pancreatic adenocarcinoma in combination with gemcitabine at doses up to 0.6 mg/day, and in 28 patients with metastatic colorectal cancer at doses up to 0.8 mg/day.

Edema, fatigue, nausea, dizziness and fever were the most common AEs seen these 6 Phase 2 studies. Most of these AEs were either Grade 1 or 2 in nature. Most common Grade 3/4 AEs included dyspnea, neutropenia, fatigue and hypotension. None of the deaths in any of these studies were attributed to BXCL701.

Antitumor activity was shown by an objective response of PR in 7/54 patients in advanced CLL patients. Two objective responses (1 complete response [CR] and 1 PR) were reported in 33 evaluable patients, for a response rate of 6.1% (2/33) in advanced melanoma. The response rate was 9.1% (5/55) in advanced NSCLC patients in combination with docetaxel. Response rate was 8.1% (6/74) in advanced melanoma patients in combination with cisplatin and 5.9% in advanced pancreatic cancer patients.

1.3.4 Phase 3 Studies

Two Phase 3 studies were conducted with BXCL701, both in advanced NSCLC patients, in combination with docetaxel and pemetrexed respectively. In both these studies, BXCL701 0.2-mg tablets were administered orally twice daily.

Similar to the AE profile seen in Phase 1 and 2 studies, edema and fatigue were the most common AEs seen in these 2 Phase 3 studies and were Grade 1 or 2 in nature. Thrombocytopenia and febrile neutropenia were the most common SAEs seen. A few cases of cardiac tamponade were also seen in both the trials. In the study with docetaxel, there was a significant difference with respect to efficacy between the 2 treatment groups in favor of placebo. In the study with pemetrexed, there was no significant difference in the 2 treatment arms with respect to efficacy. No deaths were attributed to BXCL701 during these trials.

1.3.5 Clinical Pharmacokinetics

BXCL701 has negligible protein binding in vitro. It is not metabolized to any appreciable extent and does not inhibit any of the pharmacologically relevant CYP enzymes tested in standard in vitro models. In humans, C_{max} of BXCL701 is achieved approximately 1 to 1.5 hours after oral dosing. C_{max} and area under the plasma concentration-time curve (AUC) tend to increase proportionally with increasing dose. Co-administration of BXCL701 with a high-fat meal resulted in approximately a 30% decrease in mean plasma levels (C_{max}).

1.4. Pembrolizumab

Pembrolizumab is a humanized monoclonal antibody that binds to the PD-1 receptor with high affinity, thereby blocking the PD-1 receptor-ligand interaction and boosting the immune response against tumor cells. Pembrolizumab was initially approved for the treatment of refractory melanoma in 2014 (United States Food and Drug Administration [FDA]) and 2015 (European Medicines Agency). Subsequent approvals have included subsets of non-small cell lung cancer, squamous cell carcinoma of the head and neck, classical Hodgkin lymphoma, primary mediastinal large B-cell lymphoma, urothelial carcinoma, gastric cancer, cervical cancer, hepatocellular carcinoma, Merkel cell carcinoma, and any unresectable or metastatic solid tumor with certain genetic anomalies (mismatch repair deficiency or microsatellite instability-high). The safety profile of pembrolizumab includes adverse events (AE) related to increase immune activation and include pneumonitis, hepatitis, nephritis, colitis, and hormonal dysfunction. Full details are available in pembrolizumab Prescribing Information.

2 STUDY OBJECTIVE(S)

2.1 Primary Objectives

- The primary objectives of the study are:
- To evaluate response rate per RECIST and iRECIST in patients treated in cohort A and in patients treated in cohort B.[19, 20] Tumor measurements will be in QIAC.
- To evaluate dose-limiting toxicities (DLT) in the first 6 patients enrolled to the study.

2.2 Secondary Objectives

- The secondary objectives of the study for cohort A and cohort B include:
- To evaluate progression-free survival (PFS)
- To evaluate duration of response
- To evaluate overall survival (OS)
- To evaluate overall safety and tolerability

2.3 Exploratory Objectives

- To evaluate the quantitative and qualitative effects of BXCL701 in combination with pembrolizumab on relevant immune effector cytokines in blood
- To evaluate the quantitative and qualitative effects of BXCL701 in combination with pembrolizumab on various immunological effector cells, including neutrophils, myeloid derived suppressor cells (MDSCs), dendritic cells, cancer associated fibroblast (CAF), T-cells and macrophage density in pre-dose tumor biopsies and when feasible in post-dose tumor tissues.
- To explore the predictive value of baseline PD-L1 tumor expression and tumor mutation burden (TMB) with clinical outcomes
- To evaluate changes in serially collected blood circulating tumor DNA (ctDNA) to assess for tumor response and clonal evolution
- To evaluate pre- and post-treatment PD-L1 PET/CT as a predictive tool for therapeutic efficacy.

3 STUDY DESIGN

This is an open-label, single-institution, Phase 2 study to determine the response rate of BXCL701 administered orally and daily, combined with pembrolizumab, in patients with

advanced solid cancers. The study will also assess other efficacy parameters, such as PFS, OS and DOR, as well as the safety the combined treatment. Bayesian optimal phase 2 (BOP2) design will be adopted to monitor efficacy. The study will consist of 2 stages:

[figure not shown]
- Lead-in Stage (first 6 patients enrolled) in which the safety and tolerability of the combination of BXCL701 administered orally twice a day on Days 1 to 14 of a 21day cycle plus pembrolizumab 200 mg administered intravenously (IV) on Day 1 every 21 days will be assessed and confirmed in patients with advanced solid cancers. The dose of BXCL701 will be 0.6 mg divided in two doses (0.3 mg twice a day).
- 2) Efficacy Stage (BOP2-Stage) in which patients with advanced solid cancers will be treated with BXCL701 combined with pembrolizumab. Patients enrolled to the Lead-in Stage will be also evaluated in the efficacy stage. Starting from Protocol version 7, new patients enrolled will be administered BXCL701 at the starting dose of 0.2 mg orally twice a day for the first 7 days. If well tolerated and in the absence of signs and symptoms of clinically significant hypotension the dose will be escalated to 0.3 mg orally twice a day.

During the Lead-in Stage, patients will be observed for dose-limiting toxicity (DLT) during Cycle 1. Six patients will be treated initially with 0.3 mg BXCL701 twice a day (Days 1 to 14) plus pembrolizumab 200mg:

- If > 1 of the 6 original patients has a DLT in Cycle 1, the dose will be considered above the maximum tolerated dose (MTD) and additional 6 patients will be treated at the 0.4 mg BXCL701 daily Days 1 to 14 dose level.
 - If ≤ 1 of the patients experience a DLT, the Efficacy Stage can commence
 - \circ If > 1 of the patients experience a DLT, a discussion will be held between the investigators and supporters as to how to proceed

The study schema is presented in Figure 1.

DLT = dose-limiting toxicity; pembro = pembrolizumab; PR, partial response; CR, complete response

All safety data from all patients, who received at least one dose of study drug will be included in safety analysis. Unless doses were held because of DLT, a patient must have

received >70% of their BXCL701 in Cycle 1 (i.e., \geq 30 of 42 planned doses) with pembrolizumab dosed on Day 1 of Cycle 1 to be eligible for DLT assessment.

Toxicities will be assessed by the investigator using the National Cancer Institute Common Terminology Criteria for Adverse Events (NCI CTCAE), version 5. The relationship of an AE to combination therapy (i.e., attribution to BXCL701 and/or pembrolizumab) is to be assessed by the investigator using the criteria in the protocol (Section 5.3.1).

A DLT is defined as any of the following AEs occurring during Cycle 1, regardless of investigator attribution to study treatment, unless the AE can be clearly and incontrovertibly attributed to an extraneous cause (e.g., disease progression) by the Principal Investigator:

- Any Grade 4 laboratory abnormality, regardless of duration.
- Any Grade 3 laboratory abnormalities if associated with clinical symptoms regardless of duration
- Any Grade ≥3 non-hematologic AE, with the exceptions of Grade ≥3 nausea, vomiting, diarrhea, constipation, and fatigue, that resolves to Grade ≤1 within 72 hours with optimal medical management and/or supportive measures.
- Grade ≥3 thrombocytopenia with Grade >1 bleeding or requirement for platelet transfusion.
- Grade \geq 3 febrile neutropenia.
- Grade ≥ 3 fever.
- Grade ≥ 3 skin rash.
- Laboratory abnormalities meeting Hy's law criteria (aspartate aminotransferase [AST] or alanine aminotransferase [ALT] >3 × upper limit of normal [ULN] with concomitant total bilirubin >2 × ULN).
- Any toxicity resulting in \geq 30% held/skipped doses of BXCL701 during Cycle 1.
- Delay of Cycle 2 by ≥ 14 days due to toxicity.
- Any other significant toxicity considered by the investigator and supporter's medical representatives to be dose-limiting.

Efficacy Stage:

After assessment of the safety and confirmation of the BXCL701/pembrolizumab2 dose schedule to be used in the subsequent stage, the Efficacy Stage will begin. Eligible patients will receive oral BXCL701 daily on Days 1 to 14 of a 21-day cycle plus pembrolizumab 200 mg administered IV on Day 1 every 21 days.

Study Design Features (Both Stages):

In both Lead-in and Efficacy Stages, patients will be screened for study eligibility within 28 days before the first study drug dose after provision of written informed consent. Patients who are determined to be eligible, based on Screening assessments, will be enrolled in the study on Cycle (C)1, Day (D)1 (Baseline, before the first dose of BXCL701).

During treatment, patients will attend study center visits and have study evaluations performed as detailed in the Schedule of Assessments (Appendix A). All study visits will

be conducted on an outpatient basis but may be conducted on an inpatient basis per the investigator's judgement.

All patients must have pre-treatment (prior to study treatment dosing) imaging (computed tomography [CT] scan of chest/abdomen/pelvis or magnetic resonance imaging [MRI] for baseline tumor measurements, as well as bone scintigraphy [BS, if deemed necessary]). Patients with skin, subcutaneous or lymph node metastases may also have tumor evaluations (including measurements, with a ruler) by means of physical examination. Patients with a history of central nervous system (CNS) malignant involvement or CNS symptoms should have either CT or MRI imaging of the brain performed to assess active CNS malignancy.

Tumor measurements and disease response assessments (CT or MRI; BS) are also to be performed at the end of Cycle 3 (approximately 9 weeks after the first study treatment dose), and then approximately every 9 weeks thereafter until development of progressive disease (PD). Intervals can be shortened to 6 weeks if clinically necessary per treating physician. For patients with evidence of disease control (stable disease or better) at Week 27, tumor measurements and disease response assessments may be performed less frequently (approximately every 12 weeks) thereafter. Tumor measurements and disease response assessments also are to be performed at the End of Treatment (EOT) visit.

Study procedures are listed in Appendix A.

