6.1 BXCL701 Dosage and Administration

BXCL701 tablets contain valine-proline boronic acid formulated as the methanesulfonate salt. Current dosage strengths include 0.1 mg and 0.05 mg tablets for oral administration.

BXCL701 will be administered orally as 0.1 mg and 0.05 mg tablets. BXCL should not be taken on an empty stomach. For a dose of 0.3 mg, patients will take 3 x 0.1 mg tablets and together. Patients will take 0.3 mg of the study drug twice a day, on days 1 to 14 of each cycle, for a total daily dose of 0.6 mg. BXCL701 will be continued until disease progression or unacceptable toxicity. Starting from Protocol version 7, newly enrolled patients will be administered BXCL701 at the starting dose of 0.2 mg (2 x 0.1 mg) orally twice a day. If well tolerated and in the absence of signs and symptoms of clinically significant hypotension the dose will be escalated to 0.3 mg (3 x 0.1 mg) orally twice a day.

To minimize risk of hypotension, patients should be advised to maintain adequate hydration while on-treatment, such as drinking at least 2 liters of fluids per day, including fluids with electrolytes. Factors such as strenuous exercise, heat, humidity, fever, gastrointestinal disturbance may increase hydration needs. Administration of at least 1L of IV fluids is recommended if not medically contraindicated at Cycle 1 Day 1. It is at the investigator's discretion to provide IV hydration during in-person clinic visits beyond Cycle 1 Day 1.

On days when pharmacodynamic studies are being performed, BXCL701 should be administered at the study center, and should be administered at (approximately) the same time of day on each treatment day in the cycle. In cycles in which pharmacodynamics are not evaluated, BXCL701 also should be administered at (approximately) the same time of day on each treatment day in the cycle, preferably 0800 hours. If the patient forgets to take study medication the dose will be skipped.

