7 DATA ANALYSIS AND STATISTICAL CONSIDERATIONS

This is a phase 2, single center, basket study of oral BXCL701 daily on days 1-14 in combination with intravenous PD1/PDL1 antibody on day1 of 21-day cycle in subjects with advanced and refractory malignancies. Lead-in cohort will enroll 6 patients. Only the 6 patients treated at the selected dose during safety lead-in will be assigned to Cohort A or B as appropriate. That is, if there is a dose de-escalation during safety lead-in, then the 6 patients treated at the higher dose will not be assigned to the phase II cohorts. Cohorts A and B will enroll 9 to 17 patients. Response assessments with CT and/or MRI will be done every 9 weeks (3 cycles) following RECIST and iRECIST criteria.[19, 20] Intervals can be shortened to 6 weeks (2 cycles) if clinically necessary per treating physician.

The study will follow the BOP2 design with the following operating characteristics.

Power: 0.80

Type I error: 0.05

P0:0.05**P1:**0.25

Each cohort will enroll 9 patients. If there is no complete (CR) or partial response (PR) in the first 9 patients the enrolment to that cohort will stop. If there ≥ 1 PR or CR in the first 9 patients the enrollment will continue to enroll total of 17 patients. PR or CR does not require confirmation. The treatment will be considered promising for further exploration if ≥ 3 CRs or PRs are observed in 17 patients. The expected **Sample Size** will range from 9 (if terminated after safety lead in) to 34 patients. Accounted for ~20% of patients not being evaluable for efficacy, the actual number of patients to be recruited for the trial will range from 11 to 42.

Scenarios (PA, PB)	Pr(reject H0 for cohort A)	Pr(reject H0 for cohort B)	Average sample size for cohort A	Average sample size for cohort B
(0.05,0.05)	0.046	0.046	12.0	12.0
(0.05,0.25)	0.046	0.813	12.0	16.4
(0.25,0.25)	0.813	0.813	16.4	16.4
(0.05,0.15)	0.046	0.455	12.0	15.1
(0.15,0.15)	0.455	0.455	15.1	15.1
(0.15,0.25)	0.455	0.813	15.1	16.4

Operating characteristics:

Note: PA is the response rate for cohort A, PB is the response rate for cohort B.

The Investigator is responsible for completing toxicity/efficacy summary reports and submitting them to the IND office Medical Affairs and Safety Group for review. These should be submitted as follows:

• Lead-In Stage:

After the first 6 evaluable patients, complete cycle 1 of study treatment. IND Office approval must be obtained prior to advancing to the efficacy stage.

• Efficacy Stage:

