12 APPENDIX A: STUDY SCHEDULE OF ASSESSMENTS

Screen Period			Cycle 1						Cycle	2			>C	ycle 2		EOT Visit ^a	FU Visit ^b	
Screen/Cycle Day (D):	D-28 to D-1	D1 ⁱ	D2	D5 ^t	D8 ^r	D14	D15 ^r	D1°	D2	D8 ^r	D14	D15 r	D1°	D8	D14	D15		
Informed consent	X																	
Inclusion and exclusion criteria	X	Х																
Demographics	X																	
Adverse Event Assessment	X	Х	Х	X	X		Х	Х		Х		Х	Х				Х	Х
Concomitant Medications	X	Х	Х	X	X		Х	Х		Х		Х	Х				Х	Х
cancer treatment history	X																	
Archival tumor collection ¹	X																	
Imaging and Other																		
CT/MRI	X												X ^d				X ^d	
Tumor assessment	X												X ^d				X ^d	
Study Drug Administration																		
BXCL701 administration				Day	1-14				Day	1-14			D	ay 1-	14			
Ambulatory monitoring of blood pressure before each dose of BXCL701				Day	1-14			Day 1-14					Day 1-14					
Oral hydration monitoring				Day	1-14			Day 1-14					D	ay 1-	14			
Daily safety telephone calls			Da	y 3-4,	Day 6	-14												
Pembrolizumab administration ^j		Х						Х					Х					
Clinical Procedures																		
Physical examination	X	Х	Х	Х	X		Х	Х		Х		Х	Х				Х	
Medical history/current medical conditions	X	Х	Х	Х	Х		Х	Х		Х		Х	Х				Х	
ECOG performance status	Х	Х	Х	Х	Х		Х	Х		Х		Х	Х				Х	

	Screen Period		(Cycle	1		Cycle	2			>C	ycle 2	EOT Visit ^a	FU Visit ^b				
Screen/Cycle Day (D):	D-28 to D-1	D1 ⁱ	D2	D5 ^t	D8 ^r	D14	D15 ^r	D1°	D2	D8 ^r	D14	D15 r	D1 ^c	D8	D14	D15		
Vital signs (BP, HR, body temperature, RR, O2 saturation)	X	Х	X	X	X		X	Х		Х		Х	Х				Х	
Height	Х	Х	Х	Х	Х		Х	Х		Х		Х	Х				Х	
Weight	X	Х	Х	Х	Х		Х	Х		Х		Х	Х				Х	
Clinical Laboratory Tests ^q																		
Hematology (CBC plus differential [5-part or auto- analyzer])	X	Х			X		Х	Х		X		Х	Х	X ^v		Xv	Х	
Serum chemistry ^e	Х	Х			Х		Х	Х		Х		Х	Х	Xv		Xv	Х	
Liver function tests ^f	X	Х			X		Х	Х		Х		Х	Х	Xv		Xv	Х	
T3, FT4, TSH	Xu												Xu				Xu	
Cytokine-12 panel		Х	Х	Х														
Urinalysis	Х	Х						Х					Х				Х	
Serum collection ^g		Х	Х			Х	Х	Х	Х			Х						
Whole blood collection for immune parameters ^k		Х					Х	Х				Х					Х	
Tumor biopsies ^m	X ^m									X ^m							X ^m	
Blood collection for ctDNA ^s		X ^h	X ^h		X ^h		Х	\mathbf{X}^{h}					X ^h				Х	
Pregnancy test	X ⁿ	X ^{o,p}						X°					Xº					

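### The DLT-evaluability rule asks for at least 30 of 42 BXCL701 doses in Cycle 1, but the stated schedule contains only 28

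*Combined protocol and SAP*

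**What the plan says.** Section 3 opens the evaluability rule with an exemption, "Unless doses were held because of DLT, a patient must have", and then sets the requirement: "received >70% of their BXCL701 in Cycle 1". A parenthesis introduced by i.e. restates this as at least "30 of 42 planned doses". Pembrolizumab on Day 1 is also required.

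The schedule to which the rule applies appears in three places:

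- Section 3, Lead-in Stage: "Six patients will be treated initially with 0.3 mg BXCL701 twice a day (Days 1 to 14".
- Section 6.1: "Patients will take 0.3 mg of the study drug twice a day, on days 1 to 14 of each cycle".
- Appendix A: BXCL701 administration and the row "Ambulatory monitoring of blood pressure before each dose of BXCL701" are both marked for Days 1 to 14 only.

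Section 7 ties progress to evaluable patients. A toxicity/efficacy report is due "After the first 6 evaluable patients, complete cycle 1 of study treatment", and IND Office approval is needed before the Efficacy Stage starts.

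**The concern.** The parenthesis is offered as the meaning of the percentage, yet it requires more doses than the schedule provides. If the count is taken as governing, no patient is eligible for DLT assessment except those exempted because a DLT caused doses to be held. Fully dosed patients without a DLT would drop out of the denominator, and six evaluable patients could not be assembled from those who tolerate treatment.

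What is at stake is the composition of the DLT-evaluable set, and probably the lead-in report in Section 7. The primary DLT objective (Section 2.1) and the de-escalation rule (Section 3) refer to the first six enrolled or original patients, so they do not depend on the count as worded. No response boundary or BOP2 operating characteristic depends on it either.

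**Working it through.** **Inputs**

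- Percentage threshold: more than 70% of Cycle 1 BXCL701 (Section 3).
- Printed count: at least 30 of 42 (Section 3).
- Dosing: 2 doses per day for 14 days (Sections 3 and 6.1; dosing days also in Appendix A).
- Tablets: "For a dose of 0.3 mg, patients will take 3 x 0.1 mg tablets" (Section 6.1).

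**Step 1. Reproduce the printed count.** The minimum is the smallest whole number k with k/N > 0.70. For N = 42, 0.70 × 42 = 29.4, so k = 30 (30/42 = 71.4%; 29/42 = 69.0%). The 30 fits the 42, so the conflict lies between the denominator and the schedule.

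**Step 2. Count the scheduled doses.** N = 2 × 14 = 28. Then 0.70 × 28 = 19.6, so k = 20 (20/28 = 71.4%; 19/28 = 67.9%).

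**Step 3. Compare.** The maximum possible is 28, below the required 30 (28/42 = 66.7%). The printed cut-off is 30 − 20 = 10 doses above the one implied by the percentage. For a patient with no DLT-related hold:

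| Doses received (of 28) | By percentage | By printed count |
|---|---|---|
| 0 to 19 | not evaluable | not evaluable |
| 20 to 28 | evaluable | not evaluable |

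**Step 4. Look for a reading that gives 42.**

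- Twice daily on all 21 days: 2 × 21 = 42. Not scheduled anywhere.
- Three doses a day for 14 days: 3 × 14 = 42. Not scheduled anywhere.
- Once daily: 14 doses over 14 days, or 21 over 21 days. Neither is 42.
- Tablets under Section 6.1: 3 × 28 = 84.
- Step-up dosing from Protocol version 7 changes the amount per intake, not the number of intakes, so N stays 28.
- Make-up doses (Section 6.2) replace missed doses, and doubling up is barred, so the total cannot pass 28.

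**Step 5. Check the companion DLT criterion.** Section 3 also counts as a DLT any toxicity that leads to 30% or more of Cycle 1 doses being held or skipped. On 28 doses this is 9 or more (0.30 × 28 = 8.4). If 42 were used as the denominator it would be 13 or more (0.30 × 42 = 12.6).

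**The case against.** The strongest reply is that the percentage is the operative rule and the parenthesis only illustrates it. A fully adherent patient then satisfies the rule and merely contradicts its illustration. The percentage also works well on 28 doses. Receiving at least 20 means missing at most 8, and the companion DLT criterion starts at 9 missed for toxicity, so the two rules meet without a gap. This stands, and it is why the lead-in is not necessarily unworkable. But the protocol does not say that the percentage prevails, and the count contradicts it for every patient the percentage would accept.

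Second, Section 7 neither defines evaluable nor cites the count. That also stands: the link to the IND Office report is plausible but inferred.

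Third, 42 may have an innocent origin. Section 1.3.4 records 0.2 mg tablets in the earlier Phase 3 studies, and 0.6 mg a day as three such tablets for 14 days is 3 × 14 = 42 tablets. This could explain the figure but does not rescue it. Section 6.1 lists only 0.1 mg and 0.05 mg tablets for this trial, and the parenthesis speaks of doses.

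Finally, it could be called a clerical slip with little effect. The effect is limited, but this is a threshold in a safety-evaluability rule that cannot be met as printed, which is more than a matter of style.

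**Conclusion.** The concern holds. The count requires 30 doses where the stated schedule allows 28, and no reading of the current text gives 42. The percentage and the count conflict for all totals from 20 to 28 doses. The result rests only on the schedule in Sections 3 and 6.1 and the dosing days in Appendix A, with no outside assumption. The practical effect is limited if the percentage is applied alone. It would be serious only if the count were enforced, and the documents do not show which form was used. This should be fixed, but it does not undermine the design.

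**What to change.** Reconcile the parenthesis in Section 3 with the schedule in Sections 3 and 6.1 and Appendix A. If twice-daily dosing on Days 1 to 14 stands, the protocol's own percentage corresponds to at least 20 of 28 planned doses, and the parenthesis should say so. The same denominator should be used for the criterion on held or skipped doses. Section 7 should state whether its evaluable patients are those meeting this rule.

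If any lead-in evaluability decisions have already been made, confirm which form of the rule was applied and record it.

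The cost is a one-line correction plus a short clarification in Section 7. It adds no patients or procedures, and no change to dose, schedule or DLT criteria is proposed.
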